## 6.3 Discontinuation/Withdrawal Criteria

### 6.3.1 Discontinuation of Study Treatment

Discontinuation of study treatment does not represent withdrawal from the study.

As certain data on clinical events beyond study treatment discontinuation may be important to the study, they must be collected through the subject's last scheduled follow-up, even if the subject has discontinued study treatment. Therefore, all subjects who discontinue study treatment prior to completion of the protocol-specified treatment period regimen will still continue to participate in the trial as specified in Sections 6.1.3 and 6.1.3.2.

Subjects may discontinue study treatment at any time for any reason or be dropped from the study treatment at the discretion of the investigator should any untoward effect occur. In addition, a subject may be discontinued from study treatment by the investigator or Merck if study treatment is inappropriate, the trial plan is violated, or for administrative and/or other safety reasons. Specific details regarding procedures to be performed at study treatment discontinuation are provided in Sections 6.1.3 and 6.1.3.2.

A subject must be discontinued from study treatment but continue to be monitored (see Sections 6.1.3 and 6.1.3.2) in the study for any of the following reasons:

- The subject or subject's legally acceptable representative requests to discontinue study treatment
- There is evidence of unequivocal disease progression without evidence of clinical benefit during the adjuvant treatment period (i.e., postoperative pembrolizumab-based therapy)
- There is(are) unacceptable AE(s), which requires discontinuation from study treatment at that time (the subject may still be consented to post-treatment tissue collection, if safe and feasible)
- General or specific changes in the subject's condition render the subject unacceptable for further treatment in the judgment of the investigator
- Any progression or recurrence of any malignancy, or any occurrence of another malignancy that requires active treatment
- Any AE requiring discontinuation outlined in Section 5.2
- Subject has a confirmed positive serum pregnancy test
- For subjects who are discontinued from study treatment but continue to be monitored in the trial, all visits and procedures, as outlined in the trial flowchart (Section 6.2), should be completed.

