- The first dose of study treatment following CN/MET may be no sooner than 3 weeks and no later than 6 weeks following surgery, to allow for postoperative recovery (adequate wound healing and recovery from any postoperative complications) as assessed by the treating surgeon. Subjects who cannot resume therapy within 42 days for any reason will discontinue study participation, any exception will be discussed with the PI and approved on a case-by-case basis.

At the time of disease progression (or death, unacceptable toxicity, or withdrawal of consent, whichever occurs first) on postoperative pembrolizumab-based therapy, subjects will discontinue study participation. Prior to study discontinuation, all subjects will be consented for an additional optional tissue collection.

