## 7 Reporting and Documentation of Results

### 7.1 Evaluation of Efficacy: Antitumor Effect - Solid Tumors

Subject eligibility will be determined using local assessment (Investigator assessment) based on RECIST 1.1. RECIST 1.1 will also be used by the investigator as the primary measure for assessment of tumor response, date of PD, and as a basis for all protocol guidelines related to disease status (e.g., discontinuation of study treatment).

Only those subjects who have measurable disease present at baseline have received at least 1 treatment with pembrolizumab-based therapy, and have had their disease re-evaluated, will be considered evaluable for response. Subjects who exhibit objective disease progression prior to the end of Cycle 1 will also be considered evaluable.

While either CT or MRI may be utilized, as per RECIST 1.1, CT is the preferred tumor imaging technique in this study. For the abdomen and pelvis, contrast-enhanced MRI may be used when CT with iodinated contrast is contraindicated, or when mandated by local practice. Images (including via other modalities) that are obtained at an unscheduled time point to determine disease progression, as well as imaging obtained for other reasons, but which demonstrate radiologic progression, should also be reviewed by the Investigator. MRI is the strongly preferred modality for imaging the brain. The same imaging technique regarding modality, ideally the same scanner, and the use of contrast should be used in a subject throughout the study to optimize the reproducibility of the assessment of existing and new tumor burden and improve the accuracy of the assessment of response or progression based on imaging.

Although RECIST 1.1 references a maximum of 5 target lesions in total and 2 per organ, this protocol allows a maximum of 10 target lesions in total and 5 per organ, if clinically relevant to enable a broader sampling of tumor burden.

If the Investigator identifies radiographic progression per RECIST 1.1, treatment should continue until PD has been verified.

RECIST guideline version 1.1 is published in the European Journal of Cancer:

E.A. Eisenhauer, P. Therasse, J. Bogaerts, L.H. Schwartz, D. Sargent, R. Ford, J. Dancey, S. Arbuck, S. Gwyther, M. Mooney, L. Rubinstein, L. Shankar, L. Dodd, R. Kaplan, D. Lacombe, J. Verweij. New response evaluation criteria in solid tumors: Revised RECIST guideline (version 1.1). Eur J Cancer. 2009 Jan;45(2):228-47.

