### 7.1.3 Response Evaluation Following Surgery

Following CN/MET, little to no residual tumor may be present. Progressive disease is defined as the growth of the primary tumor or appearance of any new tumors following CN/MET as assessed by the Investigator per RECIST 1.1.

Objective response (PR and CR) should be confirmed in subjects with residual disease following CN/MET by a repeat imaging assessment. The imaging for confirmation of response may be performed no earlier than 4 weeks after the first indication of a response is observed. Subjects will then return to the regular imaging schedule, starting with the next scheduled imaging time point. Subjects who receive additional imaging for confirmation do not need to undergo the next scheduled tumor imaging if it is less than 4 weeks later; tumor imaging may resume at the subsequent scheduled imaging time point.

First evidence of PD by RECIST 1.1 should be confirmed by repeat imaging assessment at 4-8 weeks in clinically stable subjects. Clinically stable subjects may continue study treatment until the repeat imaging assessment to confirm PD. In clinically unstable subjects, per the investigator's assessment, neither repeat imaging assessment nor continuation of study treatment may be feasible or in the best interest of the subject.

See section 7.1.6 for further details regarding RECIST 1.1 response criteria.

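### For a first PD scan on postoperative treatment, 6.3.1, 7.1 and 7.1.3 give treatment instructions that cannot all be followed, and nothing says whether progression means first or verified PD

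*Combined protocol and SAP*

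**What the plan says.** Section 6.3.1 sets out the cases in which "A subject must be discontinued from study treatment but continue to be monitored". Two entries in that list concern progression. One is narrow: "There is evidence of unequivocal disease progression without evidence of clinical benefit during the adjuvant treatment period". The other is broad: "Any progression or recurrence of any malignancy, or any occurrence of another malignancy that requires active treatment". The list closes by asking that, for subjects who stop treatment but stay under observation, "all visits and procedures, as outlined in the trial flowchart (Section 6.2), should be completed".

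Section 7.1 makes investigator-assessed RECIST 1.1 the measure for the date of PD and for decisions on stopping treatment, and adds: "If the Investigator identifies radiographic progression per RECIST 1.1, treatment should continue until PD has been verified". It sets no condition on clinical stability.

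Section 7.1.3, which covers the period after surgery, asks for a repeat scan at 4-8 weeks to confirm a first PD in clinically stable subjects, and says: "Clinically stable subjects may continue study treatment until the repeat imaging assessment to confirm PD". For unstable subjects it accepts that neither the repeat scan nor further treatment may be feasible or in their interest.

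Section 3.1 says that at progression "on postoperative pembrolizumab-based therapy, subjects will discontinue study participation". Section 7.1.2 lists progression among the events that end imaging.

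Section 7.1.6 defines PD without a confirmation step. Table 9 asks for more than 4 weeks' confirmation of CR and PR, and for none in the case of PD. DFS and PFS are secondary endpoints in 2.2.2 and 8.1. Section 8.4.3 reports them descriptively, with Kaplan-Meier medians. Section 8 contains no rule for dating PD or for censoring.

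**The concern.** A subject on postoperative therapy has a scan that meets RECIST 1.1 PD for the first time. The investigator has to decide that day whether to give the next dose, whether to book a repeat scan, and whether the subject stays in the study. The protocol answers each question more than once, with different answers, and no section is said to prevail.

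Two things are at stake. One is exposure to study drug after radiographic progression. The other is the DFS/PFS event. The study is open-label, the investigator assesses progression, and the choice of section would be made with the scan already in view. An event definition that leaves room for choice at that moment weakens even a descriptive estimate.

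**Working it through.** There is no stated figure to reproduce. The check sets the sections side by side for one first PD scan on postoperative treatment.

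| Section | Treatment | Repeat scan or imaging | Participation |
|---|---|---|---|
| 6.3.1, broad entry | must stop | not mentioned | stays monitored |
| 6.3.1, narrow entry | must stop only if PD is unequivocal and without clinical benefit | not mentioned | stays monitored |
| 7.1 | should continue until verified | verification implied, no interval | not addressed |
| 7.1.3, stable | may continue | repeat at 4-8 weeks | not addressed |
| 7.1.3, unstable | may not be feasible or appropriate | may not be feasible or appropriate | not addressed |
| 3.1 | ends with participation | not mentioned | ends at progression |
| 7.1.2 | not addressed | imaging ends at progression | not addressed |

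1. *Clinically stable subject.* Stopping satisfies 6.3.1 and is compatible with the permissive wording of 7.1.3, but departs from 7.1. Continuing satisfies 7.1 and 7.1.3, but breaches the broad entry of 6.3.1. No action satisfies all three.
2. *Clinically unstable subject.* The broad entry says stop. Section 7.1, read alone, says continue. Section 7.1.3 allows that continuing may be inappropriate. The conflict between 6.3.1 and 7.1 remains.
3. *The two entries in 6.3.1.* Every case that meets the narrow entry also meets the broad one. The narrow entry therefore does no work, although its wording suggests that it was meant to limit when treatment stops.
4. *Whether the repeat scan happens.* Postoperative imaging is every 2 cycles, and a cycle is 6 weeks: 2 × 6 = 12 weeks. A repeat at 4-8 weeks falls between scheduled scans, so it has to be arranged separately. If progression in 3.1 and 7.1.2 means the first PD scan, participation and imaging have ended before it is due.
5. *Exposure.* Assume that the PD scan coincides with Day 1 of a 6-week cycle. If confirmation comes before week 6, one pembrolizumab dose depends on the section followed. If it comes after week 6 and up to week 8, two doses do. In Cohort B, 28-56 days of axitinib are also involved (4 × 7 = 28; 8 × 7 = 56).
6. *Event date.* If confirmed PD is dated at the first scan, the shift is zero. If it is dated at the repeat scan, the shift is 28-56 days, that is 4-8 weeks. The plan does not settle which date applies after a confirmation step. It also does not say how a first PD is counted if the repeat scan is not done or does not bear it out.
7. *Follow-up after PD.* The abstract, 3.5 and 6.1.3.2 provide a safety visit at 30 days (+7 days). The closing entry of 6.3.1 asks for all flow-chart visits. Footnotes q and r of Table 7 list progression among the ways that treatment ends, and then send subjects into the 1-year follow-up. Section 6.1.3.3 and the Table 7 column heading reserve that follow-up for subjects who complete treatment.

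**The case against.** The strongest reply is that the sections can be read together. If progression in 3.1 and 6.3.1 means PD that has been verified, treatment and participation run on to the repeat scan and then stop. Section 7.1.3 is then the specific postoperative rule that qualifies the general one in 7.1. This reading is coherent, but the documents never state it. The broad entry in 6.3.1 points the other way, and nothing ranks 7.1.3 above 7.1. On the same view the two entries in 6.3.1 overlap rather than clash, since stopping satisfies both. That is fair, and it is why the narrow entry is called redundant here.

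It can also be said that the final words of the broad entry, on active treatment, qualify the whole of it. Progression of advanced renal cell carcinoma would ordinarily still fall within it.

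The reply has more force on follow-up. Section 6.3.1 ties its monitoring to 6.1.3 and 6.1.3.2, and the 30-day visit there fits with participation ending at progression. What remains is the closing entry of 6.3.1 and footnotes q and r.

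A reader might go further and infer that a first PD without confirmation leaves the subject event-free. No section says so, and the PD definition in 7.1.6 and Table 9 ask for no confirmation. A reader might also infer that 3.1 requires participation to end at the first scan. It does not say which scan it means. Finally, a reader might set 4-8 weeks against the 15.1-month median PFS in section 1.2.2.1. That figure comes from a different trial with a different time origin, whereas this plan reports DFS/PFS following surgery, so the ratio does not transfer.

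**Conclusion.** The concern holds for progression found during postoperative treatment. The mandatory stop in 6.3.1 and the instruction to continue in 7.1 are incompatible at a first PD scan, and 7.1.3 gives a third answer that depends on clinical stability. The missing definition of progression in 3.1 and 7.1.2 puts the repeat scan at risk, and leaves the recording of DFS/PFS events open to the section chosen.

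The size is limited. The date shift of at most about 4-8 weeks assumes dating at confirmation, which no section directs. DFS and PFS are descriptive, and 8.4.1 even groups them with exploratory endpoints. The primary endpoint uses tissue taken at surgery or biopsy, before any postoperative progression, so it, the sample size and the interim rule are untouched.

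It would be too strong to say that every postoperative progression is affected. A progression found in the follow-up year involves no study treatment to stop or continue. Preoperative PD has its own rules in 3.1 and 6.3.2. The trial is single-center, so the inconsistency would arise between investigators or between subjects, not between sites.

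**What to change.** Reconcile 3.1, 6.3.1, 7.1, 7.1.2, 7.1.3, Table 9 and footnotes q and r of Table 7 to one rule. It should say whether progression means first or verified PD for treatment, for imaging and for participation, in clinically stable and in unstable subjects. The content of that rule, including when treatment and participation end, is for the sponsor to choose. Keep in 6.3.1 only the entry on progression that matches it, and state one follow-up schedule after PD.

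For the DFS/PFS analysis, add to section 8 that PD, once established, is dated at the first scan meeting RECIST 1.1 PD. Add also that PD which cannot be confirmed because of clinical instability, death or new therapy counts as an event on that first date.

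The cost is amendment wording in the places named and a short addition to section 8. No scan is needed beyond the repeat scan that 7.1.3 already calls for.

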### 6.3.2 Withdrawal from the Study

A subject must be withdrawn from the study if the subject or subject's legally acceptable representative withdraws consent from the study.

A subject must be withdrawn from the study if there is evidence of unequivocal disease progression without evidence of clinical benefit during the preoperative treatment period. Subjects with PD during the preoperative treatment period who, in the opinion of the treating physician and principal investigator, are likely to benefit from CN/MET AND in whom surgery is safe and feasible, may proceed with CN/MET on study. Subjects in whom CN/MET is unlikely to provide benefit OR surgery is not safe and feasible, may still be consented to core tumor biopsy on study, if safe and feasible and, in the judgment of the treating physician, the biopsy will not delay appropriate standard of care. Subjects will withdraw from study participation following CN/MET or tumor biopsy. If CN/MET and tumor biopsy are not safe and feasible and not in the best interests of the subject, the subject will withdraw from study participation immediately.

If a subject withdraws from the study, they will no longer receive study treatment or be followed at scheduled protocol visits.

### 6.3.3 Lost to Follow-up

If a subject fails to return to the clinic for a required study visit and/or if the site is unable to contact the subject, the following procedures are to be performed:

- The site must attempt to contact the subject and reschedule the missed visit. If the subject is contacted, the subject should be counseled on the importance of maintaining the protocol-specified visit schedule.
- The investigator or designee must make every effort to regain contact with the subject at each missed visit (e.g., phone calls and/or a certified letter to the subject's last known mailing address or locally equivalent methods). These contact attempts should be documented in the subject's medical record.

Note: A subject is not considered lost to follow-up until the last scheduled visit for the individual subject. The amount of missing data for the subject will be managed via the pre-specified data handling and analysis guidelines.

## 6.4 Usage of Concurrent/Concomitant Medications/Vaccinations

Medications or vaccinations specifically prohibited in the exclusion criteria are not allowed during the ongoing trial. If there is a clinical indication for any medication or vaccination specifically prohibited during the trial, discontinuation from trial therapy or vaccination may be required. The investigator should discuss any questions regarding this with the Merck Clinical Director. The final decision on any supportive therapy or vaccination rests with the investigator and/or the subject's primary physician. However, the decision to continue the subject on study treatment requires the mutual agreement of the investigator, Merck, and the subject.

#### 6.4.1 Acceptable Concomitant Medications

All treatments that the investigator considers necessary for a subject's welfare may be administered at the discretion of the investigator in keeping with the community standards of medical care. All concomitant medication will be recorded on the case report form (CRF) including all prescription, over the counter (OTC), herbal supplements, and IV medications and fluids. If changes occur during the trial period, documentation of drug dosage, frequency, route, and date may also be included on the CRF.

All concomitant medications received within 28 days before the first dose of trial treatment and 30 days after the last dose of trial treatment should be recorded. For stool correlative analysis, it should be noted if antibiotics were taken within 90 days before the first dose of study drug(s). Concomitant medications administered after 90 days following the last dose of trial treatment should be recorded for SAEs and ECIs as defined in Section 7.3.5.

#### 6.4.2 Prohibited Medications

Subjects are prohibited from receiving the following therapies during the Screening and Treatment Phase (including retreatment for post-complete response progression) of this trial:

- Antineoplastic systemic chemotherapy or biological therapy not specified in this protocol
- Immunotherapy not specified in this protocol
- Chemotherapy not specified in this protocol
- Investigational agents other than pembrolizumab
- Radiation therapy
  - Note: Radiation therapy to a symptomatic solitary lesion or to the brain may be allowed at the investigator's discretion.
- Live vaccines within 30 days prior to the first dose of trial treatment and while participating in the trial. Examples of live vaccines include, but are not limited to, the following: measles, mumps, rubella, varicella/zoster, yellow fever, rabies, BCG, and typhoid vaccine. Seasonal influenza vaccines for injection are generally killed virus vaccines and are allowed; however, intranasal influenza vaccines (e.g., FluMist®) are live attenuated vaccines and are not allowed
- Systemic glucocorticoids for any purpose other than to modulate symptoms from an event of clinical interest of suspected immunologic etiology. The use of physiologic doses of corticosteroids may be approved after consultation with Merck.
- Rifaximin or lactulose to control encephalopathy
- Strong inhibitors of CYP3A4/5 (e.g. ketoconazole, grapefruit or grapefruit juice)

- Strong/moderate inducers of CYP3A4/5 (e.g. rifampin, dexamethasone, phenytoin, carbamazepine, rifabutin, rifapentine, phenobarbital, St. John's wort, bosentan, efavirenz, etravirine, modafinil, naftilin)\*
- \* Subjects enrolled on Arm A (pembrolizumab monotherapy), who may require the use of any CYP3A4/5 inducer, may be permitted to do so for clinical management of symptoms as determined by the Investigator. These medications are prohibited in Arm B (pembrolizumab + axitinib).

Subjects who, in the assessment by the investigator, require the use of any of the aforementioned treatments for clinical management should be removed from the trial. Subjects may receive other medications that the investigator deems to be medically necessary.

The Exclusion Criteria describes other medications which are prohibited in this trial.

There are no prohibited therapies during the Post-Treatment Follow-up Phase.

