### 6.1.2 Treatment Period

Subjects who experience unequivocal disease progression without clinical benefit during the preoperative treatment period or withdraw consent will be removed from the study (see Sections 6.1.3 and 6.1.3.2). Subjects who have unacceptable toxicities during the pre-operative treatment period or decline continued therapy will discontinue treatment but continue to be followed on study (Section 6.3).

#### 6.1.2.1 Preoperative Therapy, Cycle 1 Day 1

Preoperative Cycle 1 Day 1, week 1 ( $\pm 3$  days) study procedures:

- Directed physical examination
- Vital signs and weight
- ECOG performance status

- Evaluation of AEs
- Concomitant medications
- CBC with differential and platelet count\*\*
- Blood chemistry assessment\*\*, including:
  - ALP, ALT/AST, total bilirubin, calcium, phosphorus, BUN, creatinine, total protein, albumin, fasting glucose, potassium, sodium, chloride, bicarbonate, uric acid, LDH
- Coagulation assessment (PT, PTT, INR)\*\*
- Blood for correlative studies (including immune monitoring)
- Treatment:
  - Cohort A:
    - Pembrolizumab 200 mg IV (Day 1)
  - Cohort B:
    - Pembrolizumab 200 mg IV (Day 1)
    - Axitinib (Days 1-21); 5mg BID PO

\*\*Note: Laboratory evaluations may be omitted if they were already performed within 7 days of Cycle 1, Day 1

#### 6.1.2.2 Preoperative Therapy, Cycle 2 Day 1

Preoperative Cycle 2 Day 1, week 4 ( $\pm 3$  days) study procedures:

- Directed physical examination
- Vital signs and weight
- ECOG performance status
- Evaluation of AEs
- Concomitant medications
- CBC with differential and platelet count
- Blood chemistry assessment, including:

- ALP, ALT/AST, total bilirubin, calcium, phosphorus, BUN, creatinine, total protein, albumin, fasting glucose, potassium, sodium, chloride, bicarbonate, uric acid, LDH
- Thyroid Function Tests: TSH, FT4, T3
- Blood for correlative studies (including immune monitoring)
- Urinalysis, (including microscopic exam, if abnormal results are noted)
- Treatment:
  - Cohort A:
    - Pembrolizumab 200 mg IV (Day 1) Q3W
  - Cohort B:
    - Pembrolizumab 200 mg IV (Day 1) Q3W
    - Axitinib (Days 1-21). Dose titration per "Treatment Plan" in select patients, see Section 5.1.

#### 6.1.2.3 Preoperative Therapy, Cycle 3 Day 1

Preoperative Cycle 3 Day 1, week 7 ( $\pm$ 3 days) study procedures:

- Directed physical examination
- Vital signs and weight
- ECOG performance status
- Evaluation of AEs
- Concomitant medications

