#### **6.1.2.5 Cytoreductive Nephrectomy and/or Metastasectomy**

Complete the following tests within 14 days of CN and/or MET:

- CBC with differential and platelet count
- Blood chemistry assessment, including:
- ALP, ALT/AST, total bilirubin, calcium, phosphorus, BUN, creatinine, total protein, albumin, fasting glucose, potassium, sodium, chloride, bicarbonate, uric acid, LDH
- Thyroid Function Tests: TSH, FT4, T3
- Coagulation assessment (PT, PTT, INR)
- Immune parameter assessments
- Urinalysis, (including microscopic exam, if abnormal results are noted)

Subjects will undergo CN and/or MET no sooner than 2 weeks following the final cycle of preoperative pembrolizumab-based therapy. The final cycle of preoperative therapy concludes after the conclusion of the last day (21st day) of the 3rd cycle of pembrolizumab-based therapy. A window of 7 days will be allowed for surgical planning and scheduling (thus, CN and/or MET will occur 14 days [+7 days] following the final cycle of preoperative therapy). Complete the following procedures on the day of surgery:

- CN and/or MET (performed per standard of care).
- Tissue collection for study purposes (see Laboratory Manual for details).
- Pathology assessment (as clinically indicated, per standard of care).

The subject may be consented for core tumor biopsies if CN and/or MET cannot be performed following preoperative pembrolizumab-based therapy for any reason, including:

- Unequivocal disease progression
- AEs
- Development of a concurrent, unrelated medical illness that deems subject inoperable
- Subject withdrawal of consent
- Investigator or surgeon deems inoperable for any reason
- Subjects may be consented for multiple tumors to be biopsied if safe and feasible.
- Subjects who achieve a radiographic CR and have locally advanced disease will proceed with CN.

Subjects who become ineligible for CN and/or MET while on study, and do not consent to provide a tumor biopsy (if safe and feasible), will be removed from study. See section 8.2.2 for details regarding replacement policy.

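### Section 6.4.2 tells sites to remove subjects who need a prohibited treatment from the trial, against Section 6.3.1, which keeps early stoppers in follow-up

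*Combined protocol and SAP*

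**What the plan says.** Section 6.4.2 lists therapies barred during screening and treatment. It then says that subjects who, in the investigator's assessment, "require the use of any of the aforementioned treatments for clinical management should be removed from the trial". The same section closes by stating that nothing is prohibited once a subject is in post-treatment follow-up.

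Section 6.4 covers the same situation. If a prohibited drug or vaccine is clinically indicated, "discontinuation from trial therapy or vaccination may be required", and "the decision to continue the subject on study treatment requires the mutual agreement of the investigator, Merck, and the subject".

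Section 6.3.1 sets the general rule: "Discontinuation of study treatment does not represent withdrawal from the study", and "all subjects who discontinue study treatment prior to completion of the protocol-specified treatment period regimen will still continue to participate in the trial". For those who stop treatment but stay under observation, "all visits and procedures, as outlined in the trial flowchart (Section 6.2), should be completed". Section 6.1.2 applies the same idea before surgery: subjects with unacceptable toxicity, or who decline further therapy, "will discontinue treatment but continue to be followed on study".

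Section 6.3.2 names two grounds for mandatory withdrawal: withdrawn consent, and unequivocal preoperative progression without clinical benefit. Withdrawal ends both study treatment and scheduled visits.

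**The concern.** A site coordinator whose subject needs a strong CYP3A4/5 inhibitor, a live vaccine, or steroids for a non-immune reason will look in 6.4.2, because the list is there. The instruction found there is removal from the trial. Taken at its word, it stops the scans that supply DFS/PFS status, although the subject has neither progressed nor withdrawn consent.

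Two things make such a loss undesirable. It is avoidable, because 6.3.1 already describes how to stop drug and keep following. It may also be informative, because some listed drugs could be needed to manage toxicity. Subjects who received continued therapy remain evaluable for DFS/PFS under Section 8.4.1, so their missing status becomes early censoring in the Kaplan-Meier estimate or an unknown in the 1-year rate.

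**Working it through.** The plan gives no figure on this point, so the check is a comparison of text plus one short count.

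**1. What literal removal does.** Under 6.3.2 a withdrawn subject has no more scheduled visits. Under 7.1.2 imaging ends at withdrawal. For removals not due to progression, death or adverse events, Section 3.5 provides a safety visit within 30 days. Adverse event follow-up and reporting continue under 7.5 and 7.8. Safety data are therefore kept and scans are not.

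**2. Whether the discontinuation sections agree.** They do not. 6.3.1 keeps all early stoppers in the trial, and prohibited medication is not among the two grounds in 6.3.2. Usage elsewhere does not settle what removal means. Section 7.5 uses similar words for subjects with unacceptable adverse events, whom 6.1.2 and 6.3.1 keep in follow-up. Section 6.1.2.5 uses them for subjects who cannot have surgery and refuse biopsy.

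**3. Whether removal protects anything.** The prohibition covers screening and treatment only. A subject who stops study drug and enters follow-up may take the needed medicine without breaching 6.4.2. Leaving the study adds nothing to stopping the drug.

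**4. Who is affected.** For a new anticancer therapy, 7.1.2 stops imaging in any case, so nothing further is lost. 6.4.2 also makes allowances for some radiation, for physiologic corticosteroids, and for CYP3A4/5 inducers in the monotherapy cohort. That leaves mainly strong CYP3A4/5 inhibitors, inducers in Cohort B, live vaccines, and systemic steroids given for non-immune reasons.

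**5. How much follow-up per subject.** Inputs are 12-weekly visits for up to one year after the last dose or discontinuation (6.1.3.3, Table 7), 42-day cycles, and 9 cycles for the one-year treatment period.
- Scheduled visits: 52 / 12 = 4.3, so four, at weeks 12, 24, 36 and 48 after the last dose.
- 1-year mark (Section 8.1, end of the one-year treatment period): 9 × 6 = 54 weeks from the first postoperative dose.
- 2-year mark: 54 + 52 = 106 weeks.
- Example, assuming the last postoperative dose is at week 6: scans at 6 + 12k for k = 1 to 4, that is weeks 18, 30, 42 and 54. The fourth scan reaches the 1-year mark. The 2-year mark is not reached in this example with or without a change.
- If the last dose is instead the first postoperative one (week 0), the fourth scan falls at week 48, which is 54 − 48 = 6 weeks short of the 1-year mark.

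**6. A dependency.** Sections 3.5 and 6.1.3.3, and the Table 7 follow-up column, name subjects who complete 9 or 18 cycles. 6.3.1 asks early stoppers to complete the flowchart visits, and visit timing runs from last dose or discontinuation. That implies that early stoppers are included but does not say so. If the 12-weekly schedule is for completers only, rewording 6.4.2 alone recovers none of the four scans.

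**The case against.** The best defence is that the protocol already answers the question. 6.3.1 lets the investigator or Merck stop study treatment when it is inappropriate or the trial plan is violated. That plausibly covers the need for a prohibited drug, and the subject then stays in the trial. 6.3.2 does not list this ground. Because the protocol uses removal loosely, the harmless reading (off treatment, not off study) is available. What stands of this is that 6.3.1 and 6.3.2 show which rule should prevail. They do not delete the contrary instruction in 6.4.2.

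A reader might also infer that 6.4.2 and 6.4 are irreconcilable on whether study treatment must stop. The documents do not support that. 6.4.2 says should rather than must, and 6.4 requires three-party agreement before treatment continues. Together they read as a default of stopping with an agreed exception. Any rewording ought to keep that default.

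It is also fair to object that DFS/PFS are reported descriptively (Section 8.4.3), that no rate of affected subjects is available, and that the scan count rests partly on the separate ambiguity about early stoppers. All three are accepted and limit the size of the point.

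**Conclusion.** The conflict with 6.3.1 and 6.3.2 is real and worth correcting, but its reach is modest. It concerns occasional subjects who need a listed drug that is not an anticancer agent, and it bears on descriptive DFS/PFS. The number of subjects is unknown and probably small. Per subject, the ceiling is four scans, on the assumption that the 12-weekly schedule applies to early stoppers. That toxicity drives the loss is possible but not established.

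Two stronger readings should be resisted. A reader might infer that preoperative removal costs the post-treatment specimen and so harms the primary endpoint. 6.4.2 states no tissue route, but Section 6.1.2.5 does: "The subject may be consented for core tumor biopsies if CN and/or MET cannot be performed following preoperative pembrolizumab-based therapy for any reason". Section 5.1.2.2 also sends Cohort B subjects whose toxicity requires discontinuation to surgery. No effect on the primary endpoint is shown.

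A reader might also try to sort the steroids in Tables 5 and 6 into those covered by the 6.4.2 exception and those not. The exception refers to events of clinical interest, and Section 7.3.5 lists only overdose and a liver-test pattern under that term. The text does not support saying that immune-related events are plainly covered and infusion reactions are not. For Grade 3 or 4 infusion reactions, Table 6 ends study drug anyway.

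**What to change.** In 6.4.2, replace removal from the trial with: *discontinued from study treatment (unless continuation is agreed under Section 6.4) and followed per Section 6.3.1*. This keeps stopping as the default and leaves the agreed exception where it is.

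In 6.1.3.3 and the Table 7 follow-up column, add that the 12-weekly visits also apply to subjects who stop treatment early. 6.3.1 already implies this, but the recovery of up to four scans is not assured until it is written down.

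The cost is one phrase and one clause at the next amendment. No new visit type, procedure or analysis is created. Early stoppers would attend visits that 6.3.1 already points to. Which treatments are prohibited remains the sponsor's decision.
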